7.5 Analysis of Demographic and Baseline Characteristics

Demographic characteristics at Phase C baseline including age, race, ethnicity, gender, weight, height, and body mass index (BMI) for the randomized subjects will be summarized by descriptive statistics (frequency, mean, median, standard deviation, maximum, minimum, and percentage when applicable).

Disease severity and psychiatric history at Phase C baseline will also be summarized by descriptive statistics for the Safety Sample to identify any potential lack of balance between the treatment groups for the Phase C efficacy sample.

7.6 Safety Analysis

Standard safety variables to be analyzed include AEs, clinical laboratory tests, vital signs, ECGs, and physical examinations. In addition, data from the following safety scales will be evaluated: assessments of suicidality (C-SSRS) and EPS (eg, the SAS, AIMS, and BARS). Safety analysis will be conducted based on the Safety Sample defined in Section 7.2. In general, baseline of a safety variable is defined as the last observation of

Protocol 331-201-00079

the variable before taking the first dose of IMP, unless specified otherwise. Prospectively defined criteria will be used to identify potentially clinically relevant abnormal values for clinical laboratory tests, vital signs, ECGs, and body weight. Details of safety analyses will be provided in the SAP.

7.6.1 Adverse Events

7.6.1.1 Phase A

Deaths, serious TEAEs, and AEs leading to discontinuation from trial or trial treatment during Phase A will be listed for the Phase A Safety Sample.

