3.2.2 Brexpiprazole + Antidepressant Treatment Dosing Regimen

Acute Treatment Phase (Phase A): Subjects will receive single-blind brexpiprazole + open-label ADT for 6 to 8 weeks. Subjects will be titrated to a target dose of brexpiprazole over a 2- to 4-week period. Thereafter, subjects who had not met response criteria as defined in the blinded addendum, did not have potentially dose-related adverse events (AEs), and had not achieved the maximum dose of medication can have their dose increased up to 3 mg. Dose decreases can occur at scheduled or unscheduled visits once a dose of 3 mg is achieved. Subjects not able to tolerate the minimum specified target dose of 2 mg/day will be discontinued. The intention of this dosing paradigm is to have subjects treated at a maximum tolerated dose of brexpiprazole during the Acute Treatment Phase to optimize an efficacious response.

No adjustments to ADT doses are allowed in Phase A without approval from the medical monitor and changes may not be made within 5 days of a change in brexpiprazole dose.

The Acute Treatment Phase dosing schedule for brexpiprazole (flexible dosing with lead-in titration) is presented in [Table 3.2.2-1](#).

Stabilization Phase (Phase B): Eligible subjects who have completed Phase A and enroll in the Stabilization Phase will receive single-blind brexpiprazole + open-label ADT for 12 weeks. Brexpiprazole dose decreases can occur at scheduled or unscheduled visits, but dose increases can occur only at scheduled visits. The dose of brexpiprazole must be stable for the last 4 weeks of the Stabilization Phase. Subjects not meeting stability criteria will be discontinued from the trial.

No adjustments to ADT doses are allowed in Phase B without approval from the medical monitor and changes may not be made within 5 days of a change in brexpiprazole dose.

No dose adjustments to the ADT are allowed in the last 4 weeks of Phase B.

Double-blind Randomized Withdrawal Phase (Phase C): Eligible subjects who have completed the Stabilization Phase will be randomized into the Double-blind Randomized Withdrawal Phase to brexpiprazole or placebo + open-label ADT in a 1:1 ratio for up to 26 weeks. Subjects randomized to brexpiprazole +ADT should maintain the doses of brexpiprazole that they were receiving at Week 20 of the Stabilization Phase. A one-time

Protocol 331-201-00079

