7.6.5 Other Safety Data

Descriptive statistics will be provided for change from baseline to end of phase in SAS, AIMS, and BARS scores for Phases A, B and C, separately. Results will be summarized by visit. In addition, change from end of Phase B to end of Phase C in scores for the SAS, AIMS, and BARS scales will be evaluated using ANCOVA with baseline value as covariate and treatment as factor. The OC data sets will be used in the analyses of these EPS scales.

Suicidality monitored during the trial using the C-SSRS will be summarized as number and percentage of subjects reporting any suicidal behavior, ideation, behavior by type (4 types), ideation by type (5 types), and treatment-emergent suicidal behavior and ideation.

8 Management of Investigational Medicinal Product

For full details on IMP management, please refer to the IB.¹³

Protocol 331-201-00079

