5.6 Safety Analysis

Standard safety variables to be analyzed include AEs, clinical laboratory tests, vital signs, ECGs, body weight, waist circumference, and BMI. In addition, data from the following safety scales will be evaluated: Simpson-Angus Scale (SAS) Total Score, Abnormal Involuntary Movement Scale (AIMS) Total Score, Barnes Akathisia Rating Scale (BARS), and C-SSRS.

In general, safety analysis will be summarized for Phase B safety sample and Phase C safety sample respectively. Listing of safety variables for Phase A safety sample will be

provided. Baseline for Phase A safety sample will be used as the baseline for safety analysis in Phase B as well. Baseline for Phase C safety sample is defined as the last visit with available data in Phase B prior to the first dose in Phase C.

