5.6.1 Adverse Events

All adverse events (AE) will be coded by MedDRA System Organ Class (SOC) and Preferred Term (PT). A treatment-emergent AE (TEAE) is defined as an AE which starts after start of trial medication), or an AE continues from baseline of the specific phase and becomes serious, worsening, trial drug-related or results in death, discontinuation, interruption or reduction of trial medication during this phase. The incidences of the following treatment-emergent adverse events (TEAEs) will be summarized by treatment groups:

- TEAEs by severity
- Potentially drug related TEAEs
- TEAEs with an outcome of death
- Serious TEAEs
- Discontinuations due to TEAEs

Listing and incidences of AEs above will be tabulated by treatment for Phase B safety sample and Phase C safety sample, respectively. Deaths, SAEs, and AEs leading to discontinuation from trial will be listed by phase for the enrolled sample.

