5.6.7.2 EPS Rating scales

5.6.7.2.1 Analysis of EPS Rating Scales

Descriptive statistics will be provided for change from baseline to end of phase in SAS, AIMS, and BARS scores for Phases B and C safety samples. Results will be summarized by visit. In addition, change from end of Phase B to end of Phase C in scores for the SAS, AIMS (total of the first 7 item scores), and BARS scales will be evaluated using ANCOVA with baseline value as covariate and treatment and center as factors. OC data sets will be used in the analyses of these EPS scales. In addition, analyses will be

performed using the maximum (i.e. the worst) value observed during Phase C and the last visit data to determine the change from baseline score. The ANCOVA model for change at the last visit and for change to the maximum value will include the Phase C baseline, study center and treatment group. The same analyses will be performed on the AIMS individual item scores 8, 9, and 10. In addition, incidence of BARS Global Clinical Assessment of Akathisia during Phase B and C by severity category will be provided. Analyses of these EPS rating scales will be performed for the Safety Sample.

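### No adverse-event incidence table is planned for Phase A, the first-exposure phase, and the SAP leaves out Phase A EPS and ECG summaries that the protocol plans

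*Protocol*

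**What the plan says.** **Adverse events.** Protocol 7.6.1.1 gives Phase A a listing only: "Deaths, serious TEAEs, and AEs leading to discontinuation from trial or trial treatment during Phase A will be listed". Protocol 7.6.1.2 and 7.6.1.3 then ask for incidence in Phases B and C: all TEAEs, by severity, drug-related, fatal, serious and leading to discontinuation. The SAP follows the same line. Section 5.6 states: "In general, safety analysis will be summarized for Phase B safety sample and Phase C safety sample respectively". For Phase A it adds that a "Listing of safety variables for Phase A safety sample will be" provided. Section 5.6.1 repeats the restriction for adverse events: "Listing and incidences of AEs above will be tabulated by treatment for Phase B safety sample and Phase C safety sample, respectively".

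**What Phase A is.** Exclusion criterion 27 bars anyone previously exposed to brexpiprazole, so Phase A is first exposure for all subjects. Titration takes place there, and Protocol 3.2.2 adds: "Subjects not able to tolerate the minimum specified target dose of 2 mg/day will be discontinued". Exclusion criteria 34 and 36 also stop subjects at the end of Phase A for non-response or for a clinically significant safety concern.

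**EPS and ECG.** Protocol 7.6.5 says: "Descriptive statistics will be provided for change from baseline to end of phase in SAS, AIMS, and BARS scores for Phases A, B and C". SAP 5.6.7.2.1 limits the same statistics to "SAS, AIMS, and BARS scores for Phases B and C safety samples". Protocol 7.6.4 asks for mean change and incidence of ECG changes in every phase; SAP 5.6.4 gives Phase A listings only.

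**What is planned for Phase A.** SAP 5.6.1 lists deaths, serious events and events leading to discontinuation, by phase, for the Enrolled Sample. SAP 5.2 tabulates completion and reason for discontinuation in each phase. SAP 5.6.6.1 summarises exposure.

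**The concern.** The secondary objective is the safety and tolerability of adjunctive brexpiprazole in the trial's population. Events tied to starting and titrating a drug are best seen at first exposure. Under the plan, a common event in Phase A that is neither serious nor a reason for stopping appears at most as lines in a listing, with no rate attached. Subjects in the Phase B and C tables have already passed a response criterion and at least 6 weeks on drug, so those rates describe a selected group.

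The EPS and ECG differences are a separate matter. The protocol promises Phase A summaries and the SAP does not deliver them. I found no reason given in either document.

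**Working it through.** **Step 1: the plan's own funnel.** Inputs are 1450 entering Phase A and 700 entering Phase B (Protocol 3.3.1, SAP 3.6), and 55% progression from A to B (Protocol 7.1, SAP section 4).

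- 1450 × 0.55 = 797.5, against the stated 700.
- 700 / 1450 = 48.3%, against the stated 55%.

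The two inputs do not agree, so both are carried as a range. I assume that everyone who enters Phase A takes a dose.

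**Step 2: subjects who reach no phase with a TEAE incidence table.**

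- From the counts: 1450 − 700 = 750; 750 / 1450 = 51.7%.
- From the 55%: 1450 − 797.5 = 652.5; 652.5 / 1450 = 45%.

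**Step 3: what exists for Phase A and what does not.**

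| Phase A item | Protocol | SAP |
|---|---|---|
| Deaths, serious events, discontinuation events | Listed (7.6.1.1) | Listed for all enrolled (5.6.1) |
| Reason for discontinuation | – | Tabulated by phase (5.2) |
| Other adverse events | No output named | Listing at most (5.6) |
| TEAE incidence, any category | None | None |
| EPS scales | Descriptive statistics (7.6.5) | Phases B and C only (5.6.7.2.1) |
| ECG | Mean change and incidence (7.6.4) | Listings only (5.6.4) |

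**Step 4: what a Phase A table would add.** The denominator rises from 700–798 (the largest adverse-event table now planned) to about 1450.

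- Precision at an assumed 10% incidence: 1.96 × √(0.10 × 0.90 / 1450) = 1.5 percentage points either side.
- One-sided 95% upper bound with no observed case, 1 − 0.05^(1/n): 0.43% at n = 700, 0.37% at n = 798, 0.21% at n = 1450.

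**Step 5: how far the all-treated rate could differ (illustration; rates assumed, not in the documents).** Suppose an event affects 10% of those who continue and r times that among those who do not. With f the share continuing, the all-treated rate is 10% × (f + (1 − f) × r).

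- r = 1: 10% for either f.
- r = 2: 15.2% at f = 0.483; 14.5% at f = 0.55.
- r = 3: 20.3% at f = 0.483; 19.0% at f = 0.55.

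A table limited to continuers shows 10% throughout. Part of any excess among those who leave would be discontinuation events, which are already listed.

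**Step 6: events with Phase A onset in subjects who continue.** SAP 5.6.1 dates a new TEAE from the start of trial medication, not from the start of the phase, while its worsening clause refers to the baseline of the specific phase. SAP 5.6 also uses the Phase A baseline for Phase B safety. Whether a Phase A onset in a continuing subject enters the Phase B table is therefore open. Those who never enter Phase B are excluded on either reading.

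**The case against.** The strongest reply is that this is a maintenance trial at an approved dose, with short-term controlled trials already completed (Protocol 1.2.2, 2.1 and 2.2). Phase A is uncontrolled, protocol and SAP agree on how its adverse events are handled, and the most important events are captured for everyone. Protocol 7.6 also leaves the details of safety analysis to the SAP.

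Much of this stands and limits the point. A reader might infer that early intolerance will be invisible. The documents do not support that: an adverse event that forces an exit is listed, and the exit is counted by reason in the disposition table. A reader might also take the 45–52% as the share lost to intolerance. The stated purpose of Phase A is to find responders, non-response at Week 8 ends participation, and no split of exits is given. Nor is the tolerability rule confined to Phase A, since Protocol 3.8.3.3 applies it trial-wide.

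The uncontrolled design does not justify leaving the table out. Phase B is also single-arm and receives full TEAE incidence. Both documents define a Phase A Safety Sample, adverse events are recorded at every Phase A visit, and the SAP already summarises Phase A exposure, demographics and disposition. Deferring detail to the SAP does not explain why it omits EPS and ECG summaries that the protocol specifically names.

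**Conclusion.** The point holds in a limited form. Neither document plans a Phase A TEAE incidence table, and about 652 to 750 of a projected 1450 treated subjects (45–52%) never reach a phase that has one. The missing information is the incidence of events that are neither serious nor a cause of discontinuation. The range rests on projections that the plan itself says may not hold.

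It would go too far to conclude that the safety objective is answered in only half the subjects. Listings and disposition cover everyone who enters Phase A, and the protocol plans Phase A EPS and ECG summaries. It would also go too far to say that an event confined to Phase A must show as 0% in the planned tables, because the TEAE definition leaves open how such events are counted in continuing subjects.

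The EPS and ECG differences between protocol and SAP are plain and need reconciling whatever is decided on adverse events. Overall this is a cheap improvement, not a demonstrated failure of the safety evaluation.

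**What to change.** - In Protocol 7.6.1.1 and SAP 5.6 and 5.6.1, tabulate TEAE incidence for the Phase A Safety Sample in the Phase B categories: all, by severity, drug-related, fatal, serious and leading to discontinuation. Label the tables as uncontrolled.
- In the SAP 5.6.1 definition, state in which phase an event is counted, including one that starts in Phase A in a subject who continues.
- Restore the Phase A EPS summaries in SAP 5.6.7.2.1 and the Phase A ECG summaries in SAP 5.6.4, to match Protocol 7.6.5 and 7.6.4. Phase A EPS ratings are scheduled only at baseline and Week 6, so that summary will not cover subjects who leave earlier.
- A combined Phase A and B table is optional.

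The cost is some wording and repeat runs of planned table programs on data already collected. Trial conduct, alpha and the primary analysis do not change. The downside is a few more uncontrolled tables to read.

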7.6.1.2 Phase B

All AEs will be coded by system organ class and Medical Dictionary for Regulatory Activities (MedDRA) preferred term. The incidence of the following events will be summarized:

- Treatment-emergent adverse events (TEAEs)
- TEAEs by severity
- Potentially drug-related TEAEs
- TEAEs with an outcome of death
- Serious TEAEs
- Discontinuations due to TEAEs

7.6.1.3 Phase C

The incidence of the following events will be summarized by treatment group (brexpiprazole +ADT versus placebo + ADT):

- TEAEs
- TEAEs by severity
- Potentially drug-related TEAEs
- TEAEs with an outcome of death
- Serious TEAEs
- Discontinuations due to TEAEs

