7.1 Sample Size

The primary objective of this trial is to show superiority of brexpiprazole (2 to 3 mg/day) + ADT over placebo + ADT in time to relapse of MDD signs and/or symptoms.

Time-to-relapse criteria are defined in the blinded addendum to this protocol. The 2-sided log-rank test will be used to test for statistical significance of the differences between the 2 survival curves.

Based on the results from a completed randomized withdrawal trial of olanzapine/fluoxetine combination versus fluoxetine monotherapy to assess prevention of relapse in subjects with treatment-resistant depression, it is reasonable to expect that 30% of subjects who receive placebo and 16% of subjects treated with brexpiprazole will relapse in 6 months, a hazard ratio of 0.49 (brexpiprazole + ADT versus placebo + ADT) is derived. Thus, 104 relapse events are needed in this trial to reach 95% power to test the primary hypothesis of the protocol at a 2-sided 0.05 alpha level. The sample size estimates used a 1:1 randomization ratio (brexpiprazole + ADT: placebo + ADT) which allowed 2 interim looks at 50% and 75% of events accrual time points. The O'Brian-Fleming boundaries were used for sample size calculation of the interim analysis so that the first interim analysis will be conducted when 52 relapse events are available and the second interim analysis will be conducted when 78 relapse events are available. The 2-sided alpha levels for these 2 interim analyses are 0.003 and 0.018 respectively, and the alpha left for the final analysis when 104 relapse events are available will be 0.044.

Protocol 331-201-00079

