7.4.4 Interim Analysis

Two interim analyses are planned for assessment of efficacy. These analyses are planned to be performed following a group sequential approach at approximately 50% and 75% of events accrual time points and will include all randomized subjects. The second interim analysis (at 75% of events) will be performed only if the first interim analysis is not positive. Subjects who withdraw early from the trial or who are still in the trial at the end of Week 46 will be considered as providing censored observations. The O'Brian-Fleming boundaries will be used for the interim analysis so that the first interim analysis will be conducted when 52 relapse events are available and the second interim analysis, if needed, will be conducted when 78 relapse events are available (Table 7.4.4-1).²⁸ The 2-sided alpha levels for these two interim analyses are 0.003051 and 0.018325 respectively, and the alpha left for the final analysis will be 0.044005. Additionally, a 95% confidence interval for the hazard ratio (brexpiprazole + ADT vs placebo + ADT) will be provided

Protocol 331-201-00079

using the Cox Proportional Hazard model with term of treatment in the model. If the null hypothesis is rejected at either interim analysis time point, the trial will be terminated for having achieved the primary endpoint of a significantly lower incidence with brexpiprazole + ADT compared with placebo + ADT. A separate Relapse Event Evaluation Committee will review and track each relapse event identified and documented. An Interim Analysis Plan will be developed to document the details of data flow and other logistical considerations relating to the interim analyses.

Table 7.4.4-1 Boundaries for Rejection of Null Hypothesis for Interim and Final Analyses		
Analysis	Number of events	2-sided alpha Level^a
Interim analysis #1 (~50%)	52	0.003051
Interim analysis #2 (~75%)	78	0.018325
Final analysis (100%)	104	0.044005

^aObtained using PASS 14 sample size software.

The interim monitoring of efficacy will be performed by an independent IARC (Section 3.7.7). Should the interim analysis be performed at a different time, different frequency, the spending function approach as originally introduced by Lan and DeMets²⁹ will be applied to adjust the critical values in order to guarantee an overall 0.05 alpha level. The spending functions corresponding to O'Brien-Fleming boundaries will be formally applied to the time-to-event analysis (using the log-rank test).

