3.4 Double-blind Maintenance (Phase C)

Subjects eligible for the Double-blind Randomized Withdrawal Phase (Phase C) will be randomized 1:1 to double-blind treatment with brexpiprazole + ADT or placebo + ADT for up to 26 weeks. During Phase C, subjects will be evaluated in the clinic at biweekly visits for the first 2 visits and monthly visits thereafter.

Time-to-relapse (primary efficacy endpoint) is defined as meeting any of the following criteria measured from randomization into Phase C:

- At the same visit, an increase on the MADRS total score of 50% from randomization and CGI-S score ≥ 4 , **OR**
- Hospitalization for depression, **OR**

- Discontinuation for lack of efficacy or worsening of depression, **OR**
- Active suicidality, defined as a score of ≥ 4 on the MADRS item 10 **OR** an answer of “yes” on question 4 or 5 on the Columbia-Suicide Severity Rating Scale (C-SSRS) **OR** an answer of yes to any of the questions on the Suicidal Behavior section of the C-SSRS.

Subjects meeting the criteria for relapse will be withdrawn due to lack of efficacy. In addition, functional relapse is defined as a 30% increase in Sheehan Disability Scale (SDS) mean total score from Phase C baseline and at least one SDS sub-score at 4 or greater and a SDS total score greater than or equal to 7 when all 3 sub-scores are available (or SDS total score greater than or equal to 5 when work/school item does not apply) at a Phase C visit. In the event that the SDS phase C baseline is 0, the evaluation will be based on the SDS total score and SDS sub-score. Time-to-functional relapse will be the earliest time in Phase C a subject met the above criteria. If a visit is needed between scheduled visits in Phase C, it will be considered an unscheduled visit unless the subject meets criteria for relapse in which case the visit will be considered the end of trial visit and appropriate evaluations for Week 26/End of Phase C/Relapse should occur.

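### Phase C adverse events are summarized only as crude incidence, although withdrawal at relapse would give brexpiprazole about 8% to 9% more observation time under the planning assumptions

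*Protocol*

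**What the plan says.** Protocol 7.6.1.3 lists the Phase C adverse event tables under the sentence "The incidence of the following events will be summarized by treatment group". SAP 5.6.1 has the matching sentence: "The incidences of the following treatment-emergent adverse events (TEAEs) will be summarized by treatment groups". The tables cover TEAEs by severity, potentially drug-related TEAEs, TEAEs with fatal outcome, serious TEAEs and discontinuations due to TEAEs.

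Neither document gives adverse events a person-time denominator, an exposure-adjusted rate or a time-to-first-event analysis. The only definition of an incidence rate is in the ECG section (SAP 5.6.4). It divides patients with an abnormality by patients exposed and evaluated, which is a crude proportion.

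Relapse ends participation. SAP 3.4 states: "Subjects meeting the criteria for relapse will be withdrawn due to lack of efficacy". Protocol 3.1 and the mandatory withdrawal list in Protocol 3.8.3.3 agree. Protocol 7.1 expects that "30% of subjects who receive placebo and 16% of subjects treated with brexpiprazole will relapse in 6 months".

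Two further provisions bear on the point. Every subject has a safety contact 21 (+2) days after the last dose, at which adverse events are recorded (Protocol 3.1 and 3.7.1.5). The TEAE definition in SAP 5.6.1 sets a start but no end at the last dose.

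**The concern.** In a randomized withdrawal trial that succeeds, placebo subjects leave sooner. A crude proportion treats a subject seen for 6 weeks and one seen for 26 weeks alike. Even with the same true event hazard in both arms, the arm that stays longer accumulates more subjects with an event. Part of the adverse event difference would then reflect the efficacy result.

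Safety and tolerability is the stated secondary objective (Protocol 2.3). The SAP respects unequal follow-up elsewhere: relapse, functional relapse and all-cause discontinuation are analysed as censored times. The adverse event tables do not. The question is how large the distortion is under the plan's own assumptions.

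**Working it through.** **Inputs.** Relapse within 6 months is 30% on placebo and 16% on brexpiprazole (Protocol 7.1). Phase C lasts T = 26 weeks (SAP section 4). There are 225 subjects per arm with 20% loss to follow-up (Protocol 7.1), here assumed equal in both arms. Safety follow-up is 21 days, taken as 3 weeks.

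**The plan's own figures reproduce.** Hazard ratio = ln(0.84)/ln(0.70) = 0.489, matching "a hazard ratio of 0.49 (brexpiprazole + ADT versus placebo + ADT) is derived". Schoenfeld events for a fixed design at hazard ratio 0.49, 95% power and 2-sided alpha 0.05: 4 × (1.960 + 1.645)² / (ln 0.49)² = 102.2, so 103. With the three boundaries in Protocol 7.4.4, power at 104 events is 95.0% and overall alpha is 0.0500, in line with "104 relapse events are needed in this trial to reach 95% power". Exponential times are thus a fair reading of the design.

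**Mean time on Phase C treatment.** With total exit hazard over 26 weeks H, mean time = 26 × (1 − e^(−H)) / H.

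- No other loss. Placebo: H = −ln 0.70 = 0.3567, giving 26 × 0.30/0.3567 = 21.87 weeks. Brexpiprazole: H = −ln 0.84 = 0.1744, giving 26 × 0.16/0.1744 = 23.86 weeks. Ratio 1.091.
- With 20% loss, add −ln 0.80 = 0.2231 to each H: 19.73 and 21.45 weeks. Ratio 1.087.
- Loss of 10% to 30% moves the excess only from 8.9% to 8.5%.
- At 225 per arm this is about 102.9 vs 94.3 subject-years without loss, or 92.5 vs 85.1 with 20% loss.

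**Counting the safety follow-up.** Adding 3 weeks to both arms gives 26.86/24.87 = 1.080 without loss and 24.45/22.73 = 1.076 with 20% loss. The ratio falls, but the absolute gap stays at about 2.0 weeks (1.7 with loss).

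**Effect on crude incidence when the true hazards are equal.** Let a = −ln(1 − p)/26 be the weekly event hazard, where p is the 26-week risk with full observation, and let λ = H/26 be the weekly exit hazard. On-treatment crude incidence = a/(a + λ) × (1 − e^(−26(a + λ))).

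| 26-week risk | No loss: brexpiprazole vs placebo | Difference (points) | 20% loss: brexpiprazole vs placebo | Difference (points) |
|---|---|---|---|---|
| 2% | 1.84% vs 1.68% | 0.15 | 1.65% vs 1.52% | 0.13 |
| 5% | 4.59% vs 4.21% | 0.38 | 4.13% vs 3.80% | 0.33 |
| 10% | 9.19% vs 8.44% | 0.75 | 8.28% vs 7.63% | 0.65 |
| 20% | 18.41% vs 16.93% | 1.48 | 16.63% vs 15.34% | 1.28 |

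The follow-up adds the same time to both arms, so it barely changes these differences.

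**Timing.** Over the first 4 weeks exposure differs by 1.4%, and over the first 8 weeks by 2.8%. At week 26 the ratio of subjects not yet relapsed is 0.84/0.70 = 1.20. Late-onset events carry most of the distortion.

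**The case against.** **The display is descriptive.** Both documents say that events are summarized. No test, ratio or interval for adverse events is planned. A reader might infer that a formal between-arm safety comparison is biased, but the documents contain none. This stands: the point concerns how a table will be read.

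**The gap is conditional.** A reader might infer that the design fixes a 9% imbalance. It fixes only withdrawal at relapse. The size needs the assumed relapse rates, exponential times and full follow-up. An interim stop would shorten follow-up in both arms. "The 2-sided alpha levels for these two interim analyses are 0.003051 and 0.018325 respectively"; at hazard ratio 0.49 these correspond to about a 35% chance of crossing at 52 events and about 79% by 78 events. How far the gap would then shrink depends on accrual, which the documents do not give in enough detail. This stands.

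**The effect is small against sampling error.** With 20% loss and 225 per arm, the 95% half-widths for the difference are about 2.3, 3.6, 5.0 and 6.8 points at 26-week risks of 2%, 5%, 10% and 20%. The artefact is about 0.1 to 0.4 standard errors. This stands, although the artefact has a predictable direction and grows with efficacy.

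**It does not hide harm from the drug.** Under equal hazards it inflates the brexpiprazole figure. A reader might infer that crude tables shield brexpiprazole, but the arithmetic points the other way. What can be diluted is a true excess on placebo, such as events after withdrawal.

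**Part of the information is already planned.** SAP 5.6.6.1 gives numbers treated by week and arm, and SAP 5.5.4.3 plans Kaplan-Meier curves for all-cause discontinuation. A careful reader could approximate person-time from these. However, total exposure time is not tabulated, and nothing links it to the adverse event tables.

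**Rates have their own assumptions.** Events per patient-year presume a roughly constant hazard. That is doubtful after 18 to 20 weeks of prior brexpiprazole in both arms and a half-life of about 95 hours (Protocol 1.2.1). Nor do rates remove informative withdrawal if relapse and adverse events are related. This is a good reason not to make them the main display.

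**Conclusion.** The point holds as a minor one. Phase C TEAEs are planned only as crude incidence, and under the planning relapse rates brexpiprazole subjects would be observed for longer: about 9% more time on treatment, or about 8% more when the safety follow-up is included. With equal true hazards this appears as roughly 0.1 to 1.5 percentage points more events on brexpiprazole for 26-week risks of 2% to 20%. The effect is slight for events in the first weeks and largest for late events.

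These figures rest on 30% and 16% relapse, constant relapse and event hazards, equal loss in both arms and full 26-week follow-up. They fall towards zero as the relapse rates converge, and they shrink if the trial stops early. The documents do not support a claim that the planned safety evaluation is invalid or that brexpiprazole risk is concealed.

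**What to change.** In SAP 5.6.1, add for Phase C the total patient-years by arm and first-event rates per 100 patient-years, with the between-arm rate difference or ratio, for TEAEs, serious TEAEs and discontinuations due to TEAEs. State one observation window and use it for both events and person-time: either on treatment only, or through the 21-day safety contact. Place these results beside the crude incidence table, which stays.

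The cost is a sentence or two in the SAP and one standard table. The randomization, adverse event start, discontinuation and completion dates already enter SAP derivations, and the start of double-blind dosing is defined in SAP 5.6.6.1. A footnote should say that the rates assume a roughly constant hazard and do not correct for informative withdrawal.
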